### *3.3.8 Subject Lost to Follow-up*

If a subject is lost to follow-up, the investigator should make a good faith effort to contact the subject with at least three (3) documented communication attempts (at least one of which must be in writing). The investigator should inform the subject of the option to withdraw.

If a subject relocates during the clinical trial, efforts will be made to maintain the subject in the study if reasonable travel expenses allow continued participation, provided payment of travel expenses by the sponsor is permitted by applicable law. Alternatively, the subject may be transferred to another clinical trial site, if one is available in the new geography. If the subject cannot be transferred to another clinical site, then the investigator will withdraw the subject from the study as described above.

## **3.4 Subject Care**

The following sections contain general guidance on dealing with device explant and/or replacement. Axonics does not recommend the removal of the implanted Neurostimulator except in cases of uncontrolled infection, suspected damage to surrounding tissues that may be worsening because of the implant, or intolerable side effects that are not mitigated with inactivating the system.

The decision to explant or replace an implanted device should be made by the subject with appropriate counsel by the physician on procedural risks. A qualified physician who has been trained in the implant/explant of the Axonics SNM System must perform these procedures according to the device manuals.

### *3.4.1 Implanted Lead Issues*

In the event that the implanted Tined Lead fails, migrates, or is implanted in an undesired position such that adequate therapy cannot be provided, Axonics recommends revising or replacing the lead. Tined Lead revision and replacement does not require a Neurostimulator replacement, however, the physician has the option to replace the Neurostimulator at that time. If the subject does not wish to undergo a replacement in the case of lead failure, their device should be deactivated. If a Tined Lead replacement occurs, the original activation date shall remain as Day 0.

### *3.4.2 Explanting the Neurostimulator*

In the event that a Neurostimulator needs to be surgically revised (for example, in the case of infection or significant pain at the Neurostimulator site), the device may be moved or replaced and the original activation date shall remain as Day 0.

### *3.4.3 Deactivating the Axonics SNM System*

In some cases, the subject may elect to leave the device implanted, but no longer activated. Leaving the Tined Lead and/or Neurostimulator implanted does not add significant risk to the subject.

Subjects who elect to leave a device implanted that is not activated must return their external devices to the clinical site.

### 3.5 Study Termination

#### 3.5.1 Study Completion

The study may be closed when the following occurs:

- The Enrollment Cap has been met or eighty-one (81) Trial Responders have reached the 1-month follow-up.
- All the subjects have met one of the following criteria:
  - Subject has completed the final study follow-up visit
  - Subject has a mandated or elective deactivation/explant of the device with completion of required follow-up per protocol
  - Subject is withdrawn from the study or is lost to follow-up

When a subject completes the final study visit, they will be allowed to continue to use the Axonics SNM System and be treated by their physician according to the normal standard of care.

Axonics expects that the study will run to completion prior to being closed. In the case of an unexpected issue, the following contingency plans will be enacted.

#### 3.5.2 Study Closure

If the Data Safety and Monitoring Board (DSMB) determines there is sufficient concern for subject safety and/or there is a logistical reason to discontinue the study (e.g., lack of enrollment), Axonics reserves the right to terminate the study. In the case of a safety concern, devices may be deactivated and/or explanted.

- If the study is terminated, the reasons for this decision will be documented and the information will be provided to the investigator.
- All external components must be returned to Axonics.
- Adverse events will be followed until closure or documented as chronic.

#### 3.5.3 Clinical Site Closure

Axonics, with or without advice from the DSMB, reserves the right to close a clinical site at any stage based on reasonable written notice to the investigator.

The investigator may also discontinue participation in the study with reasonable written notice to Axonics.

Should either of these events occur, the investigator shall:

- return all documents and devices to the sponsor
- provide a written statement as to why the investigator would like to discontinue participation
- notify the Ethics Committee and the regulatory authority (as applicable)
- arrange for continued follow up of already enrolled participants (as applicable)

## 4 DATA COLLECTION AND MANAGEMENT

### 4.1 Procedures and Steps

Table 1 lists the assessments required for each visit, as well as the time window for each visit. This section describes the visit requirements and each assessment.

If a subject has temporary illness or an adverse event that is likely to interfere with the interpretation of the data collection (e.g., diarrhea, common cold, urinary tract infection), then the physician may postpone the visit outside the visit window and treat the subject according to the usual standard of care. The physician shall make a determination if stimulation should be active during the temporary illness period. The visit data should be collected as soon as possible once the illness/adverse event has cleared.

If the stimulation was turned off for any reason, then the visit shall be postponed and the diary and other data collected once the stimulation has been on for at least one week. In the case that stimulation was off, it should be reactivated and remain on at all times.

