**Table 1: Study Visit Schedule**

Visit	Baseline	Implant	Activation (Day 0)	1-Week Visit (Day 7 ± 4)	2-Week Visit (Day 14 ± 4)	3-Week Visit (Day 21 ± 7)*	1-Month Visit (Day 30 ± 7)	2-Month Visit (Day 60 ± 10)	3-Month Visit (Day 90 ± 10)	6-Month Visit (PEP) (Day 180 ± 20)	9-Month Visit (Day 270 ± 30)	1-Year Visit (Day 365 ± 30)	18-Month Visit (Day 545 ± 30)	2-Year Visit (Day 730 ± 45)	Unscheduled
Informed Consent	X														
Demographics & Medical History	X											X		X	
Inclusion/ Exclusion Criteria	X														
Vital Signs	X	X	X	X	X	X	X	X	X	X	X	X	X	X	X
PHQ-15	X														
Edmonton Frail Score	X														
Adverse Event Form	X	X	X	X	X	X	X	X	X	X	X	X	X	X	X
Procedure Report		X													
Device Performance			X	X	X	X	X	X	X	X	X	X	X	X	X
72-hour Voiding Diary	X			X	X	X	X	X	X	X	X	X	X	X	X***
EQ-5D	X										X		X		X
CCCS**	X						X		X	X	X	X	X	X	
CCF-FIS***	X						X		X	X	X	X	X	X	
ICIQ-OABqol	X						X		X	X	X	X	X	X	
Subject Satisfaction with Treatment					X		X		X	X	X	X	X	X	
Medication Usage & Healthcare Utilization	X				X		X		X	X	X	X	X	X	X

\*3-week visit is not mandatory if subject is responding positively to programming and does not need reprogramming.

\*\* CCCS survey will only be asked after Baseline for patients that had a qualifying score (15 or greater) at Baseline.

\*\*\*CCF-FIS survey will only be asked after Baseline for patients that had a qualifying score (6 or greater) at Baseline.

\*\*\*\*If unscheduled visit is planned in advance, subject should be asked to complete a diary prior to the visit.

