#### *4.2.4 Device Performance Metrics*

The following items will be collected to assess performance of the Axonics SNM System, as applicable:

- Impedances on all electrodes. Impedances should be within 400 to 6000 ohms. Physicians should refer to the Clinician Programmer Manual for information on troubleshooting impedances that are not within range.
- Electrode configurations and stimulation parameters at office arrival and upon departure (after programming optimization)
- Charging history from the Neurostimulator
- Number of hours stimulation has been ON since last visit
- Subject's ability to recharge the device

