### *5.2.4 Analysis methods*

#### *5.2.4.1 Primary Endpoint*

The primary effectiveness endpoint is that the proportion of all implanted subjects that are Treatment Responders is greater than 50% at 6-months post-activation. If the proportion of Treatment Responders is statistically greater than 50%, the study will be considered to be a success.

As mentioned above, a secondary endpoint analysis will also be conducted in subjects who are "Trial Responders" to allow for a direct comparison to the published SNM literature where analysis at follow-up visits are performed only in trial responders i.e. subjects that have  $\geq 50\%$  improvement in

symptoms after a one-month trial with an external stimulator.

The primary endpoint will be tested for significance based on a one-sided binomial test (such as Fisher's exact test) at a 2.1% significance level to account for two additional early looks as detailed in the Statistical Analysis Plan.

The primary safety endpoint of the study is the rate of adverse events (AEs) through 6-months.

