###### Missing not at Random (MNAR):

Subjects that are intraoperative screen failures or explanted or withdrawn due to adverse event(s) or lack of efficacy will be considered treatment failures and their baseline diary data will be used as the primary endpoint diary data.

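### The 6-month diary is postponed without a latest date until stimulation is back on, so subjects who switched off and restarted are scored only on therapy, and no planned analysis tests this

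*Combined protocol and SAP*

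**What the plan says.** The primary endpoint (section 5.2.4.1) is that "the proportion of all implanted subjects that are Treatment Responders is greater than 50% at 6-months post-activation". Table 1 schedules that visit as "6-Month Visit (PEP) (Day 180 ± 20" days), which is Day 160 to Day 200.

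Section 4.1 contains two postponement rules.

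- For a temporary illness or an interfering adverse event, "the physician may postpone the visit outside the visit window", and the data are to be collected as soon as possible after it clears.
- For stimulation that was off, postponement is mandatory: "If the stimulation was turned off for any reason, then the visit shall be postponed and the diary and other data collected once the stimulation" resumes and runs for a minimum period. The diary is taken "once the stimulation has been on for at least one week". The section adds: "In the case that stimulation was off, it should be reactivated and remain on at all times". No reason for being off is exempted and no latest date is given.

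The responder definition in section 3.3.6 depends only on the diary at the visit; stimulation status plays no part. Under the missing-not-at-random rule in section 5.2.4.6.1, subjects "explanted or withdrawn due to adverse event(s) or lack of efficacy will be considered treatment failures", as are intraoperative screen failures. The tipping-point analysis in section 5.2.4.7 varies missing values only. Section 4.2.4 collects "Number of hours stimulation has been ON since last visit", but not the reason for any off-period.

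**The concern.** The claim concerns all implanted subjects at 6 months, but the measurement is made conditional on the therapy running. Take two subjects who switch off for the same reason, such as discomfort or lack of effect. One is explanted or withdraws and is a failure. The other stays in, restarts, completes a diary a week or more later and may be a responder.

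The stimulation-off rule can only replace an off-therapy diary with an on-therapy one, so any error it causes favours the device. The trial is single-arm and unblinded and is judged against a fixed 50% goal, so there is no control arm in which the effect could cancel.

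The planned safeguards do not detect it. The imputation rules and the tipping-point analysis act on missing data, whereas a postponed diary enters every analysis as an ordinary observation. The rule applies to every scheduled diary, so it also reaches the 1-month diary that defines Trial Responders (section 3.3.5).

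**Working it through.** **Inputs from section 5.2.2.** n = 116 implanted, null proportion 0.50, planning proportion 0.65, one-sided alpha 0.021. Section 5.2.4.1 specifies a one-sided binomial test.

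**The plan's own figure.** With null variance under the null and alternative variance under the alternative, power = Φ[(0.15 × √116 − 2.03 × 0.5) / √(0.65 × 0.35)] = 89.5%, which agrees with the stated 90% or so. For the exact binomial test, the smallest success count with tail probability at or below 0.021 is 70 of 116 (60.3%). The attained alpha is 1.6% and the exact power at 65% is 87.4%.

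**Effect of the postponement rule.** The documents give neither of the two quantities needed, so both are assumed:

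- f: share of implanted subjects who are off for discomfort, an adverse event or lack of effect, stay in and restart, and would be non-responders if scored in the window;
- q: their chance of a 50% reduction on the diary after restart.

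If π is the rate with these subjects counted as failures, the observed rate is π + f × q. For example, f = 5% (0.05 × 116 = 5.8, about six subjects) and q = 0.50 gives 0.50 + 0.05 × 0.50 = 0.525. The table shows P(X ≥ 70) for X ~ Binomial(116, 0.50 + f × q). With f = 0 or q = 0 it is 1.6%.

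| Restart response q | f = 2% | f = 5% | f = 10% |
|---|---|---|---|
| 25% | 2.1% | 3.1% | 5.4% |
| 50% | 2.7% | 5.4% | 14.4% |
| 65% | 3.1% | 7.5% | 23.0% |

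The corresponding rise in the responder rate, f × q, runs from 0.5 points (2% × 25%) to 6.5 points (10% × 65%).

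**The same question from the other side.** Suppose 65% is the on-therapy rate and the affected subjects, responding at that same rate, are counted as failures. The rate becomes 0.65 × (1 − f): 63.7%, 61.8% or 58.5% for f = 2%, 5% or 10%. Exact power falls from 87.4% to about 80%, 66% or 38%.

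**The case against.** Several points on the other side are sound.

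- **Not everyone who switches off is scored on therapy.** A reader might infer that the rule rescues all such subjects and that the rate is inflated. The documents do not support that. Explants and withdrawals for an adverse event or lack of efficacy are failures, and a subject who restarts without benefit is a non-responder under section 3.3.6. Only those who stay in, restart and then reach a 50% reduction can raise the rate.
- **The visit window need not be broken.** It spans 40 days and the restart condition is one week, so a postponed diary can still fall inside it. Only the illness rule expressly allows a visit outside the window. What stands is that no outer limit is stated.
- **The off-rate may be low.** Section 4.1.6 provides an attempted contact at about 5 months to check adherence, before the window opens at Day 160. This may reduce the number who are off at the visit, though it does not govern how they are scored.
- **The 65% restart response is generous.** It is the planning rate for all implanted subjects, applied here to a group selected for discomfort or lack of effect. At 25% and f = 2% the error stays at about the nominal 2.1%.
- **This is partly an estimand choice.** Response with the device running is a legitimate quantity, and the error rates above treat an off-therapy status as failure. That stands, but the plan states its claim for all implanted subjects, does not declare this choice, and does not test sensitivity to it.
- **Replacing the primary diary rule now is debatable.** Section 5.2.2 says all subjects are already implanted, so a change in when diaries are taken could mix two measurement rules in one cohort.

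**Conclusion.** The concern holds in limited form. Section 4.1 sets no latest date for a diary postponed because stimulation was off. Subjects who switched off for discomfort, an adverse event or lack of effect and then restarted are scored only on therapy. Any bias favours the device, and no planned analysis tests it. The responder rate may be inflated; the documents do not show that it is.

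The size cannot be computed from the documents. Over assumed off-rates of 2% to 10% and restart responses of 25% to 65%, the chance of meeting 70 of 116 at a true 50% runs from 2.1% to 23.0%, against 1.6% without the effect. These figures assume that every affected subject would be a non-responder if scored in the window; if none is affected, or none responds after restart, there is no bias. Section 5.2.4.1 refers to the statistical analysis plan for the early looks; any further provision there beyond the text supplied could not be checked.

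**What to change.** 1. State a latest date for a diary to count as the 6-month primary value, for example the end of the Day 180 ± 20 window, and handle later diaries under the missing-data rules. Say which class then applies: a subject who was off but neither explanted nor withdrawn is not named in either class of section 5.2.4.6.1. Say also how this date relates to the illness rule, which allows visits outside the window.
2. Tabulate postponed 6-month diaries by reason and length of delay.
3. Pre-specify a sensitivity analysis of the primary endpoint. It should count as non-responders all subjects whose 6-month diary was postponed because stimulation was off for a device-related, adverse-event or efficacy-related reason, or for an unknown reason. Identify off-periods from the hours-on data in section 4.2.4. Those data do not give the reason, so take it from visit and adverse-event records. Lack of effect need not appear as an adverse event (section 8.6.1, item 4), which is why unknown reasons are included.
4. The sponsor should reconcile the instruction in section 4.1 to reactivate and stay on with sections 3.4.1 and 3.4.3, which provide for deactivation. No stimulation rule is proposed here.

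The cost is some protocol and analysis-plan wording, one table, one further analysis and a review of records for reasons. The responder rate may be lower in the sensitivity analysis.

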#### 4.1.1 Enrollment & Baseline

The investigator will identify subjects for inclusion in the study using accepted medical practice (e.g. screening subject records).

A pre-screening form that is provided by the sponsor shall be completed by the investigator to ensure that there is the potential for the subject to meet the inclusion and exclusion criteria.

Only information that is available through the standard of care shall be used to complete pre-screening.

The subject must be following a stable regimen of medical/drug therapy with no anticipated changes in therapy for a period of at least six (6) months following implantation. Any changes to medical/drug therapy during the study are highly discouraged unless it becomes a medical necessity.

A urine pregnancy test will be administered if the subject is female and of child-bearing potential. Female subjects of child-bearing potential must remain on adequate contraception, including surgical sterilization, hormonal methods, intrauterine devices, barrier methods, spermicidal methods, or abstinence.

Before signing the consent form, subjects must have the potential to meet all of the inclusion criteria and none of the exclusion criteria. Only subjects identified as eligible and who have consented will be implanted with the Axonics SNM System according to the implant manuals.

Once a subject has signed the informed consent, they will begin the baseline evaluations as listed in Table 1. Baseline questionnaires and the 72-hour bladder diary should be completed and entered into the electronic database at least 7 days prior to the implant procedure date to allow for review for completeness and to ensure that the inclusion/exclusion criteria are met. Axonics reserves the right to require that the implant procedure be postponed if the data is not entered 7 days prior to the implant procedure date.

After signing informed consent, subjects will be given written and verbal instruction and may be shown instruction videos on how to complete their diaries and how to use the Axonics SNM System.

To ensure that the subjects can refer to this information as needed, subjects may be provided with an electronic tablet containing informational videos to use for the duration of the clinical study.

#### *4.1.2 Implant*

A qualified physician who has been trained on the Axonics SNM System implantation must perform the implant. In the absence of specific guidance from Axonics on surgical procedures (such as anesthesia, surgical cut-down, post-operative wound care), the physician should follow their usual standard of care.

The following are requirements of the study protocol:

- Subjects must use an antiseptic wash the night before surgery.
- Appropriate intravenous antibiotics must be administered at the time of the surgical procedure.
- Surgical procedure will be performed under general anesthesia, conscious sedation, or MAC anesthesia. Use of muscle relaxants should be avoided to allow for observation of intraoperative motor responses.
- Lead impedance measurements must be obtained and recorded at the time of implant to verify system integrity. Impedances should be within 400 to 6000 ohms. Physicians should refer to the Clinician Programmer Manual for information on troubleshooting impedances that are not within range.
- Intra-operative testing must be performed. Stimulation must evoke motor responses consistent with the S3 sacral nerve at motor thresholds less than 4mA on at least two (2) electrodes to confirm acceptable Tined Lead placement and proceed with the Neurostimulator implant. Motor threshold is defined as the lowest stimulation amplitude that provides a clear anal bellows with or without big toe flexion. Sensory threshold is defined as the lowest stimulation amplitude that provides a feeling of “tapping”, “pulling” or “tingling” in the rectum, extending forward to scrotum or vagina and/or labia. Subjects who do not provide a positive motor response to intra-operative testing will be managed according to Section 3.3.3.
- Tined Lead placement must be verified with lateral and anterior-posterior fluoroscopy. The lead must be in the S3 (preferred) or S4 foramen. An image of the lateral fluoroscopy showing the position of the tined lead must be captured and maintained by the site.
- Neurostimulator implanted no deeper than 3.0 cm below the skin.
- Neurostimulator implanted horizontally with the ceramic side farthest from the midline.
- Wound should be irrigated prior to closure.

#### *4.1.3 Activation (Day 0)*

Activation should occur between zero (0) and fourteen (14) days of the implant. On the day of stimulation activation, the following steps should be taken:

- The subject will be instructed on how to use the Remote Control and Charge System.
- Subjects should be instructed to charge the device for approximately one hour every week. Any subject that has difficulty charging the device due to post-operative pain, fluid in the pocket, or difficulty placing the charger in an effective location should be provided further training at the clinical site.
- A study card indicating the subject is enrolled in a clinical trial using an experimental device, as well as an ARTISAN-SNM Subject Therapy Guide that details the charging of the device and safety related information will be given and reviewed with each subject.
- Stimulation should be turned on and programmed to an appropriate level as described in the device manuals.
- A voiding diary should be provided with instructions given to the subject that the diary must be completed within seven (7 days) prior to the next visit.
- The evaluations listed in Table 1 must be completed.
- Subjects should be reminded to continue to take their medications as prescribed and to be consistent with their fluid intake.
- The initial programming should be set to a stimulation frequency of 14 Hz and pulse width of 210 $\mu$ s.
- The amplitude should be set to a level where the stimulation can be felt, but is not uncomfortable.
- Bipolar stimulation is recommended, with the cathode placed so that the stimulation is felt in the areas between the vagina/scrotum and the rectum and the anode placed as far from the cathode as possible.
- The subject should be advised to increase amplitude, as necessary, to ensure that stimulation can be felt.

